BIOMEDICAL RESEARCH PROTOCOL

UNIVERSITY OF MISSOURI

Project Title: Differential Efficacy of Corticosteroid Solutions for Non-Operative Treatment of Digit Flexor Tenosynovitis: A Double-Blind Prospective Randomized Clinical trial.

IRB Number: 2014039

Version Number: 2.0

Version Date: 27 JUL 2020

Principal Investigator: [name]

Background:

Idiopathic stenosing tenosynovitis of the digits, more commonly known as trigger finger, is a common cause of hand pain and dysfunction. Many previous studies have described the pathophysiology of this condition and it can be summarized as inflammation of the flexor tendons leading to a size mismatch between the tendon and the flexor pulley system. By far the most common location of this mismatch is at the A1 pulley.

The current mainstay of treatment has been:

1. Injection of corticosteroid into the area immediately surrounding the A1 pulley and flexor tendon
2. Surgical release of the A1 pulley

Several corticosteroids have been used for injection- dexamethasone, methylprednisolone, triamcinolone, betamethasone, paramethasone, etc. Less commonly used treatment strategies have included: topical NSAIDs and extracorporeal shock therapy. The typical progression of treatment is one or two steroid injections and then surgical release if injections have failed.

To our knowledge, there have been no head to head comparison studies of the efficacy of different corticosteroid formulations in preventing conversion to surgical treatment. In our study, we will look at the efficacy of two of the most commonly used steroids: triamcinolone and dexamethasone.

Objectives:

Primary outcome: Treatment success, defined as lack of conversion to surgical treatment, or no desire to proceed with surgery during study period (3 months).

Secondary outcomes: Grade of triggering (Green classification of trigger finger severity¹), QuickDASH and PROMIS Upper Extremity scores, VAS.

Study Question/Hypothesis:

We hypothesize that a 0.5 cc injection of Triamcinolone 40 mg/mL will be the most effective steroid injection for the non-surgical treatment of trigger finger.

Inclusion/Exclusion:

Inclusion criteria:

1. Adults aged 18 years and older
2. At least one symptomatic trigger finger
3. Patients recommended to receive corticosteroid injections

Exclusion criteria:

1. Previous surgeries/injections for trigger fingers in digit being treated for study
2. Participating in another clinical trial

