3. Inability to receive corticosteroid injections (i.e. allergies, adverse reactions, etc.)
4. Unable to sign informed consent
5. Pregnant or plan to become pregnant

Number of Subjects:

Approximately 200 subjects will be enrolled.

Study Procedures/Methods:

Enrollment/Randomization/Treatment Visit:

Eligible patients presenting with primary flexor tenosynovitis will be enrolled on a voluntary basis. Prior to the injection, subjects will have already completed the PROMIS and QuickDASH surveys as part of standard care.

Enrolled patients will be randomized to one of three treatment arms:

1. Triamcinolone 40mg/mL
2. Triamcinolone 10mg/mL
3. Soluble dexamethasone 4mg/mL

Each study patient will receive the appropriate corticosteroid injection in the affected digit(s), consisting of a 1:1 mixture of 1% lidocaine plain and corticosteroid, total volume 1cc.

Blinding:

Syringes will be prepared and masked with opaque tape by the clinic nurses, thus providing blinding for providers administering the injection.

Follow-Up/Clinic Visits:

Subjects will be re-evaluated at 6 weeks post-injection and, if still symptomatic, will undergo a second injection of the same corticosteroid solution. At final follow-up (12 weeks), symptomatic patients who have failed treatment after 2 injections will be offered surgical release of the A1 pulley. Subjects who refuse a second injection at 6 weeks follow-up will be offered surgery, and the reason for refusal (treatment failure) will be recorded.

The visits and all research activity will be outlined below:

6 Week Follow-Up:

- Objective Measures:
 - Grade of triggering (Green classification of trigger finger severity1)

- Subjective Measures:
 - QuickDASH
 - PROMIS scores
 - VAS
- Second Corticosteroid injection (if subject still symptomatic)

12 Week (3 Month) Follow-Up (if applicable):

- Objective Measures:
 - Grade of triggering (Green classification of trigger finger severity1)
- Subjective Measures:
 - QuickDASH
 - PROMIS scores
 - VAS

6 Month Follow-Up:

The patient will be contacted via a phone call or Patient IQ to check on the status of their condition. If they are still experiencing a degree of triggering they will be advised by their physician to return to clinic for a standard of care visit. If they are no longer experiencing triggering, they will be asked to complete a survey over the phone or through Patient IQ only.

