Specimen Collection: If a patient is recommended to undergo surgery at the end of the study, the tendon and capsule that is normally resected and discarded after surgery will be collected for analysis. After collection these tissues and data will be identified from the patient and assigned a number for use in study analysis. **We seek to only collect tissues from patients that are normally removed and discarded during trigger finger release procedures. None of the patients will undergo additional surgical procedures for the collection of tissues in this study.** For simplification purposes, potential subjects must agree to the collection of these specimens to participate in the study, even if they do not end up needing surgical intervention.

The collected tissue will be formalin-fixed and processed for histological sectioning for routine and immunohistochemical staining to assess and score degree of tissue pathology and effects of injections on treated tissue in order to effectively test the hypothesis.

Potential Risks:

There could be risk of accidental data breach/breach of confidentiality, and this will be minimized by having patient collected de-identified data locked separate from the decoder list linking subject number to patient MRN.

Potential Benefits:

Potential benefits include relief of their trigger finger pain and function. Steroid injections have been shown to provide symptom relief for patients suffering from trigger finger. We also hope to demonstrate a differential efficacy between different corticosteroid formulations, which would help guide future clinical decision-making.

Compensation:

The subjects will not be compensated for their participation in the study.

Costs:

The subjects will be financially responsible for all of their standard of care treatment and the corticosteroid injections are considered standard of care and will be billed to their insurance.

Statistics/Power:

We define a clinically significant difference in treatment efficacy as an absolute risk reduction of surgery of 20% (NNT = 5) between steroid formulations.

Based on our power calculation, 158 patients are required to have a 90% chance of detecting, as significant at the 5% level, an increase in treatment success of corticosteroid from 70% in the control group to 90% in the experimental group.

We plan to enroll 200 subjects to account for subjects that do not complete the study or are lost to follow-up.

References:

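### The sample size of 158 (200 enrolled) is a two-group figure applied to a three-arm trial, so the stated 90% power is not delivered

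*Combined protocol and SAP*

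**What the plan says.** The whole sample size justification is in the Statistics/Power section. It defines the clinically important difference as an "absolute risk reduction of surgery of 20% (NNT = 5) between steroid formulations". It then states that "158 patients are required to have a 90% chance of detecting, as significant at the 5% level, an increase in treatment success" "from 70% in the control group to 90% in the experimental group". On the margin for losses it says: "We plan to enroll 200 subjects to account for subjects that do not complete the study or are lost to follow-up".

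The Enrollment/Randomization/Treatment Visit section describes a different structure: "Enrolled patients will be randomized to one of three treatment arms". The arms are triamcinolone 40 mg/mL, triamcinolone 10 mg/mL and soluble dexamethasone 4 mg/mL. The Study Question/Hypothesis section expects that triamcinolone 40 mg/mL "will be the most effective steroid injection for the non-surgical treatment of trigger finger".

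The protocol does not say which arm is the control. It gives no allocation ratio, primary test, list of contrasts, multiplicity rule or expected dropout rate, and it does not say whether the 5% level is one- or two-sided.

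**The concern.** The power statement describes a trial with two groups, and the protocol runs one with three. If 158 is a two-group total, dividing it among three arms leaves every pair of formulations with fewer patients than the calculation requires. The 42 extra patients are assigned to non-completion, so they cannot also be counted as filling the third arm.

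This is the only power statement for the primary outcome, and the protocol hopes the result will guide clinical decisions. Readers told that the trial had 90% power could take a non-significant comparison as good evidence against a 20-point difference between two formulations. The trial would not support that degree of confidence.

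**Working it through.** **Inputs.** From Statistics/Power: success rates of 0.70 and 0.90, 5% level, 90% power, 158 required, 200 enrolled. From Enrollment/Randomization/Treatment Visit: three arms. Assumed: 1:1:1 allocation, a two-sided test (which reproduces 158) and pairwise comparisons.

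**Step 1: reproduce 158.** Two proportions, equal groups, unpooled variance:

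n per group = (1.960 + 1.282)² × (0.7×0.3 + 0.9×0.1) / 0.20² = 10.507 × 0.30 / 0.04 = 78.8, rounded up to 79.

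2 × 79 = 158, an exact match. The arcsine formula also gives 79 per group. The other standard variants do not give 158:

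- pooled variance: 82 per group, 164 in total
- pooled with continuity correction: 92 per group, 184 in total
- one-sided unpooled: 65 per group, 130 in total

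Three arms of 79 would be 237.

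**Step 2: patients per arm.** 158/3 = 52.7 and 200/3 = 66.7. Both are below 79.

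**Step 3: power for one pair, 70% v 90%, two-sided 5%.** With the formula that yields 158, power = Φ(0.20/√(0.30/n) − 1.960).

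- n = 53: 0.20/0.0752 = 2.658; Φ(0.698) = 0.758
- n = 67: 0.20/0.0669 = 2.989; Φ(1.029) = 0.848
- n = 79: Φ(1.286) = 0.901

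Other methods agree closely:

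| Per arm | Unpooled | Pooled | Chi-square, exact enumeration |
|---|---|---|---|
| 52 | 0.750 | 0.729 | 0.745 |
| 53 | 0.758 | 0.737 | 0.755 |
| 66 | 0.843 | 0.827 | 0.838 |
| 67 | 0.848 | 0.833 | 0.844 |
| 79 | 0.901 | 0.889 | 0.902 |

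Fisher's exact test is lower: 0.677 at 53 per arm and 0.792 at 67.

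**Step 4: more than one comparison.**

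| Requirement | 158 evaluable | 200 evaluable |
|---|---|---|
| One pair, Bonferroni for two comparisons (α = 0.025) | 62–66% | 74–77% |
| One pair, Bonferroni for three pairs (α = 0.0167) | 56–60% | 69–72% |
| 40 mg/mL (90%) significantly better than both others (70% each), unadjusted, simulated | about 61% | about 74% |

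**Step 5: what the numbers would support.** At 53 per arm with a 70% comparator, 90% power is reached only when the better arm succeeds in about 93–94% (exact chi-square power is 89% at 93%). Keeping 90% power for each 70% v 90% pair needs 3 × 79 = 237 completers unadjusted, 3 × 94 = 282 with Bonferroni for two comparisons, or 3 × 102 = 306 for three.

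**The case against.** The protocol never names its primary contrast, so a shortfall for equal-arm pairwise tests depends partly on assumption. Four other readings deserve a hearing.

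- **40 mg/mL against the other two arms pooled.** An unpooled 2:1 formula needs 156, close to 158, and gives 91% nominal power at 53 v 105. Exact chi-square power there is about 85%, and about 93% at 67 v 133. This is the closest the design comes to its claim. No such contrast is written down, however, and it would not show that 40 mg/mL is better than each of the others.
- **Both triamcinolone strengths against dexamethasone.** The Background speaks of comparing two steroids. Power is 82–88% at 105 v 53 and 90–94% at 133 v 67. Again, no pooling is specified.
- **Unequal allocation.** Two arms of 79 use all 158. With no losses from 200, 42 remain for the third arm, so only one pair reaches 90%.
- **An overall three-group test.** Power at 158 is 63–82%, depending on the pattern of rates. Of the patterns tried, only 70/90/90 with all 200 evaluable reaches 90%.

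The target difference is defined between formulations and the hypothesis ranks one arm above the rest; both point to pairwise comparisons. None of these readings is stated in the protocol, and none reliably gives 90% at 158.

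Two parts of the objection stand. First, 75% is the lower end of a range: it assumes that all 42 extra patients (42/200 = 21%) are lost, and no dropout rate is given. With fewer losses, power moves towards 84%. Second, the arithmetic of 158 is correct for two groups; the fault is in applying it to three.

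**Conclusion.** The concern holds. The figure of 158 is a correct two-group total that has been used as the total for three arms. Under 1:1:1 allocation and a two-sided 5% test of 70% v 90%, one pairwise comparison has about 75% power at 158 completers and about 84% if nobody is lost from 200. That is roughly 15 points and 6 points below the stated 90%, before any multiplicity adjustment. The conclusion rests on equal allocation and pairwise testing, neither of which the protocol states. The size of the shortfall changes under the alternatives, but no design written in the protocol supports 90% power at 158.

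**What to change.** Rewrite the power paragraph for the three-arm design.

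1. Replace the control and experimental labels with the actual comparison or comparisons, for example triamcinolone 40 mg/mL v triamcinolone 10 mg/mL and v dexamethasone. State the allocation ratio, the test, its sidedness and the multiplicity rule, because the power depends on all of them.
2. Remove the 90% claim and state what the planned numbers give. Suggested text, if allocation is 1:1:1: *With 158 completers (about 53 per arm), the trial has about 75% power for a single pairwise comparison of 70% v 90% success at two-sided 5%; with 200 patients and no losses (about 67 per arm) it would have about 84%.*
3. If more than one comparison is primary, add the adjusted figure: 62–66% for two comparisons or 56–60% for three, at 158 completers with Bonferroni.

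The cost is one reworded paragraph and a less favourable stated power. Enrolment need not change. If the sponsor prefers to keep 90% power for each pair, the unadjusted requirement is 237 completers, or 237/0.79 = 300 enrolled at the 21% loss that the present margin implies.

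### The hypothesis ranks triamcinolone 40 mg/mL above two other arms, but no comparison or success rule is stated and the 90% power belongs to a single two-group contrast

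*Combined protocol and SAP*

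**What the plan says.** Under Study Question/Hypothesis, the protocol predicts: "Triamcinolone 40 mg/mL will be the most effective steroid injection for the non-surgical treatment of trigger finger". Under Enrollment/Randomization/Treatment Visit, "Enrolled patients will be randomized to one of three treatment arms": triamcinolone 40 mg/mL, triamcinolone 10 mg/mL and dexamethasone 4 mg/mL. The allocation ratio is not given.

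Under Statistics/Power, a clinically significant difference is defined as an "absolute risk reduction of surgery of 20% (NNT = 5) between steroid formulations", without saying which formulations. The power statement follows: "158 patients are required to have a 90% chance of detecting, as significant at the 5% level, an increase in treatment success of corticosteroid". The rise it assumes is given as "from 70% in the control group to 90% in the experimental group". The section ends: "We plan to enroll 200 subjects to account for subjects that do not complete the study or are lost to follow-up".

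No section says which arm is the control, which pair is primary, what test will be used, how several comparisons will be handled, or what result would support the hypothesis. The definition of treatment success under Objectives applies to a patient. It is not a rule for the trial.

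**The concern.** A claim that one of three arms is best is a claim against two comparators. The power statement describes a trial with one control group and one experimental group, and those labels fit none of the three arms unambiguously. Two things are at stake.

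- **Power.** If 158 is a two-group total, dividing it among three arms leaves each comparison with fewer patients than the calculation assumed. A claim that needs two significant results has lower power still.
- **Interpretation.** With no rule written down, any one significant pair could be offered as support. Two of the arms are strengths of the same drug. A win for 40 mg/mL over dexamethasone does not show that 40 mg/mL is better than 10 mg/mL, yet nothing in the plan prevents that conclusion.

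**Working it through.** **Inputs from the protocol.** Success 70% and 90%, power 90%, 5% level, 158 patients required, 200 enrolled, three arms.

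**Assumptions.** 1:1:1 allocation and two-sided tests (neither is stated). True success is listed in the order 40 mg/mL, 10 mg/mL, dexamethasone. With 158 completers there are 158/3 = 52.7, taken as 53 per arm. If all 200 complete there are 200/3 = 66.7, taken as 67 per arm, which is the best case.

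**Step 1: reproduce 158.** For two independent proportions with unpooled variance:

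n per group = (1.960 + 1.282)² × (0.7×0.3 + 0.9×0.1) / 0.2² = 78.8, rounded up to 79.

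The total is 2 × 79 = 158, the protocol's figure. Exact power at 79 per group is 0.902. So 158 is the total for one two-group comparison.

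**Step 2: power in three arms.** Exact binomial enumeration, pooled z test at 1.96, counting only results that favour 40 mg/mL. To beat both, 40 mg/mL must be significantly higher than each of the other arms.

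| True success (%) | Result | 53 per arm | 67 per arm |
|---|---|---|---|
| 90/70/70 | one given pair | 0.755 | 0.844 |
| 90/70/70 | beats at least one | 0.89 | 0.94 |
| 90/70/70 | beats both | 0.622 | 0.747 |
| 90/75/70 | beats both | 0.468 | 0.586 |
| 90/80/70 | beats both | 0.273 | 0.347 |

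The middle-arm rates of 75% and 80% are assumptions, included to show the range.

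**Step 3: 40 mg/mL only tied for best (90/90/70).** It beats at least one arm with probability 0.755 (53 per arm) or 0.844 (67 per arm). It beats both with probability 0.024 or 0.025. The result against dexamethasone is a true difference. It misleads only if it is reported as showing that 40 mg/mL is the best of the three.

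**Step 4: all arms equal (at 70%, 80% or 90%).**

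- At least one of the three unadjusted pairs significant, in either direction: 12.0% to 12.6%.
- 40 mg/mL significantly better in at least one of its two pairs: 4.4% to 4.7%.
- 40 mg/mL beats both: 0.5% to 0.6%.

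**Step 5: size needed for 90% power to beat both at 90/70/70.** About 95 per arm, or 3 × 95 = 285 completers. The ratio 158/200 = 0.79 implies 21% loss, so 285/0.79 is about 361 enrolled.

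**The case against.** The best counter-argument is that the protocol does not commit to a single pair or to beating both arms, and other readings come closer to 90%. By the same exact test at 90% versus 70%, with 158 and 200 completers respectively:

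- 40 mg/mL against the other two arms combined (53 v 105; 67 v 133): 85% and 93%. The unpooled formula that yields 158 gives 91% at 53 v 105.
- Both triamcinolone strengths combined against dexamethasone (105 v 53; 133 v 67): 88% and 94%. The Background does frame the study as a comparison of these two drugs.
- 40 mg/mL beats at least one arm at 90/70/70: 89% and 94%.

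It can also be said that the false-positive risk in favour of 40 mg/mL is below 5% when all arms are equal, that the 12% figure includes a pair the hypothesis does not concern, and that a rule other than beating both could be prespecified.

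Much of this is fair. The error-rate concern is mild, and the size of the power loss depends on the rule. But none of these readings is written in the protocol, none reaches 90% by the exact test with 158 completers, and none would show that 40 mg/mL is the best of three. That the same data carry 62% or 89% power depending on an unwritten rule is the reason to write one.

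**Conclusion.** The concern holds. The protocol tests a best-of-three hypothesis with no stated comparison or success rule, and its 90% power with 158 patients comes from a two-group calculation that does not describe the three-arm trial. Under 1:1:1 allocation and 90/70/70, the power to beat both other arms, which is the ordinary meaning of the hypothesis, is about 62% with 158 completers and 75% if all 200 complete. A single pair also falls short, at about 75% and 84%. If the second-best arm truly succeeds more often than 70%, the power to beat both is lower.

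The main consequences are overstated power and freedom to choose the supporting comparison after the data are seen. This should be corrected before analysis.

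**What to change.** Before analysis, add a rule to Statistics/Power along these lines:

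> Triamcinolone 40 mg/mL will be concluded most effective only if its success rate is significantly higher than that of each of the other two arms, each tested at two-sided 5% with no division of alpha. Any other pairwise difference is secondary and will be reported as a risk difference with a confidence interval.

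Alpha need not be divided because both tests must succeed: with a tie for best, the rule errs about 2.5% of the time. Whether to adjust the secondary pairs for multiplicity is left to the sponsor.

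Replace the two-group power statement with the power of the three-arm design under this rule, giving the allocation ratio and the assumed success rate in each arm.

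**Cost.** Two sentences and a rewritten power statement, with no extra enrolment required. The downside is a less favourable figure: 62% to 75% at 90/70/70, 47% to 59% if the middle arm succeeds in 75%, and 27% to 35% if it succeeds in 80%. The headline claim may therefore fail even when 40 mg/mL is truly best. If the sponsor wants 90% for this rule at 90/70/70, the price is the roughly 361 enrolled shown above instead of 200.
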